4. STUDY LIMITATIONS

As an observational study, there are inherent limitations with respect to potential for alternate explanations for any observed association.

The source claims data include limitations with respect to certainty of the capture of exposure, covariates, and outcomes. As a comprehensive insurance database, essentially all billable medical services will result in claims for reimbursement, so that the certainty of capture is tied to likelihood of a claim being submitted to the insurer.

Although duration of atrial fibrillation may represent a risk factor for study outcomes, this covariate will be incompletely captured since the patient history in the dataset is relatively short (at least 12 months, and an average of approximately 2 years), and a first claim within the database may not represent atrial fibrillation onset since the condition is typically not diagnosed at its onset.

Dosing of warfarin in clinical practice is complicated, and estimating dose and duration of exposure based on healthcare utilization data is therefore challenging. The “days’ supply” field is expected to be most meaningful, but the potential for misclassification exists.

New initiators are operationally defined as patients with no use in the prior 12 months. This does not ensure, however, that patients have never used anticoagulants; the possibility remains that these patients were treated at some prior time point before they enrolled in United or insurance plans that are part of the MarketScan database.

Medication use in United Healthcare and MarketScan data - as in all administrative healthcare databases - is restricted to prescription drug medication. Consequently, the use of over-the-counter (OTC) medications (e.g., OTC aspirin) is not captured. In addition, exposure is assessed based on prescription pick-up at a pharmacy and might be misclassified in “as treated” analysis if patients do not take their medications. However, misclassification of prescription drug exposure is generally considered less than in other exposure assessment

approaches, including physician prescribing records and patient self-reporting. [[P13-03077](#); [P13-03078](#)]

6. QUALITY ASSURANCE AND CONTROL

All aspects of data analysis will be conducted according to standard procedures of the . Programming for this project will be conducted by a primary analyst and validated by a separate analyst (validation analyst). For all data processing and analysis steps, the validation analyst will review the program along with input and output data sets, and for select steps of the project will employ double programming techniques to reduce the potential for programming errors.

7. ETHICAL/SCIENTIFIC APPROVAL

This study will be submitted to the Institutional Review Board (IRB)

8. STUDY MILESTONES AND RESPONSIBILITIES

Date	Phase 3		Data Source	
	Milestone	Month	United	MarketScan
			Claims and lab data are released every 6 months in Jan and Jul (6-month lag time)	Claims data are released quarterly in Mar, Jun, Sept, and Dec (9-month lag time) Lab data are released yearly in Dec (12-month lag time)
Year 1				
Jun, 2012	Contract	0		
Jul, 2012	Draft Protocol	1		
Mar, 2013	Protocol finalization	9		
Year 2				
Jun, 2013	Draft Interim Report*	12	Jun, 2012	
Aug, 2013	Interim Report	14	Jun, 2012	
Dec, 2013	Interim Report	15	Dec, 2012	
Oct, 2014	Interim Report	20	Jun, 2013	Claims through Mar 2013 Labs through Dec 2012
Year 3				
Mar, 2015	Interim Report	27	Dec, 2013	Claims through Sep 2013 Labs through Dec 2012
Aug, 2015	Interim Report	32	Jun, 2014	Claims through Mar 2014 Labs through Dec 2013
Year 4				
Mar, 2016	Interim Report	39	Dec, 2014	Claims through Sep 2014 Labs through Dec 2013
Aug, 2016	Interim Report	44	Jun, 2015	Claims through Mar 2015 Labs through Dec 2014
Year 5				
Jun, 2017	Final Report	54	Dec, 2015	Claims through Dec 2015 Labs through Dec 2014

The reports will include a core set of analyses with corresponding tables and figures that repeat with updated data in each of the 6 monthly blocks.

The interim reports along with the draft and final reports will consist of a description of the methods, including patient selection and variable definitions. This description will be followed by tables for each of the anticoagulant medications, follow-up characteristics (including adherence) and the utilization measures of interest. The tables will be descriptive of all included medications and not include explicit comparisons. The tabular results will be followed by an interpretive summary along with a discussion of the findings and implications.

9. DISTRIBUTION OF RESULTS

Manuscripts describing this work will be submitted for publication in peer-review journals. Findings may also be submitted for presentation at scientific conferences.

10. FUNDING

Boehringer Ingelheim GmbH

11. APPENDICES

11.1 APPENDIX 1: LIST OF FIGURES AND TABLES

List of Core Tables

These tables will be generated separately for United and MarketScan; and will be presented only for incident and former users combined, unless meaningful differences between characteristics of incident and former users are observed.

- | | |
|----------|--|
| Table 1 | Treatment initiation over time |
| Table 2 | Characteristics of Anticoagulation Users: all time periods combined |
| Table 3 | Characteristics of Anticoagulation users: latest time period |
| Table 4 | Adherence metrics for Anticoagulation users: all time periods combined |
| Table 5 | Adherence metrics for Anticoagulation users: latest time period |
| Table 6 | |
| Table 7 | Characteristics of continuers, switchers (combined and by treatment switched to), and discontinuers at 3 months : characteristics measured during the 12-months preceding treatment initiation . |
| Table 8 | Characteristics of continuers, switchers, and discontinuers at 3 months: characteristics measured during the 3-months immediately preceding the event (day of switch, day of discontinuation, day 90 for continuers). |
| Table 9 | Characteristics of continuers, switchers, and discontinuers at 6 months : characteristics measured during the 12-months preceding treatment initiation . |
| Table 10 | Characteristics of continuers, switchers, and discontinuers at 6 months: characteristics measured during the 3-months immediately preceding the event (day of switch, day of discontinuation, day 180 for continuers). |
| Table 11 | Characteristics of continuers, switchers, and discontinuers at 12 months : characteristics measured during the 12-months preceding treatment initiation . |
| Table 12 | Characteristics of continuers, switchers, and discontinuers at 12 months: characteristics measured during the 3-months immediately preceding the event (day of switch, day of discontinuation, day 360 for continuers). |

List of Core Figures

[figure not shown]
These figures will be generated separately for United and MarketScan

- Figure 1: Cumulative incidence of treatment switches - 30 day gap

Figure 2: Cumulative incidence of treatment discontinuation – 30 day gap

Figure 3: Cumulative incidence of treatment switches or discontinuation – 30 day gap

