Team Member Epidemiology:					
Project Team:					
Study data source:		UnitedHealth 2009 through 2015 MarketScan 2009 through 2015			
Objectives:		The objective of this study is to provide a description of patients with non-valvular atrial fibrillation at risk for stroke initiating oral anticoagulants and a description of existing utilization patterns for warfarin and for the new oral anticoagulant (NOAC) medications as they become available over time.			
Methodology/Study design:		Observational cohort study			
Expected number of patients:		~ 200,000 (estimated size of the unmatched cohort including warfarin, dabigatran, and other NOACs)			

Main criteria for inclusion:	A recorded diagnosis of atrial fibrillation. Initiation of oral anticoagulant medication. At least 18 years of age on the date of anticoagulant initiation CHA ₂ DS ₂ -VASc score ≥ 1
-------------------------------------	--

Name of company:		
Boehringer Ingelheim GmbH		
Name of product: PRADAXA®		
Name of active ingredient: dabigatran		
Protocol date 31 July 2014	Study number 1160.177	Planned study period Jun 2012 – Jun 2017
Main criteria for exclusion:	Patients with less than 12 months enrolment in the UnitedHealth Research Database or MarketScan database preceding the date of first dispensing will be excluded. Also excluded will be patients with missing or ambiguous age or sex information. Patients with documented evidence of valvular disease. Patients with prior use of any oral anticoagulant	
Study product:	PRADAXA (dabigatran)	
Comparison group:	Warfarin, and other new oral anticoagulants as they become available	
Expected duration of exposure:	Until treatment discontinuation as observed in the data source; the study objective is to describe observed utilization	
Outcomes:	
This study will describe the patient population with non-valvular atrial fibrillation initiating oral anticoagulants and anticoagulants utilization patterns. Utilization measures include:
 
 • Number/proportion of patients initiated on specific anticoagulants and anticoagulant doses • Time until treatment discontinuation (gap > 30 days) • Time until treatment switch 	

**Data Analysis
Methods:**

Analyses are inherently descriptive in nature. Utilization patterns will be examined overall

The initial analyses will be based on currently available data from Jan 2009 – Jun 2012. Subsequent analyses will include additional data in 6-month increments (Jul 2012 – Dec 2015).

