3.2 STUDY POPULATION

From the UnitedHealth Research Database and MarketScan source data, we will identify patients with a recorded diagnosis of non-valvular atrial fibrillation at risk for stroke who initiated anticoagulant medications between January 2009 and June 2012. Additional increments of data will be added as they become available (in 6 month intervals). Data from the time period before dabigatran was launched will be used to describe the characteristics of warfarin patients before the availability of NOAC, and to evaluate a potential shift in characteristics of warfarin patient over time as NOAC enter the market.

Inclusion criteria²:

- Any person within the source data who had a diagnosis of atrial fibrillation recorded (ICD-9 Dx code of 427.31, atrial fibrillation) and received a dispensing of an anticoagulant medication (warfarin and dabigatran for the initial analysis; with others to be added as they become available for stroke prevention in later time intervals) in the timeframe of the study.
- The first dispensing is preceded by at least 12 months continuous enrollment in the study database, defined as <32 days enrollment gap using enrollment and disenrollment dates. The study will thus focus on 'new initiators' defined operationally as no dispensing of any anticoagulant in the prior 12 months. Note that new initiators will turn into prevalent users over time.
- Patients' follow-up will end when there is a treatment gap of ≥ 30 days. If the same patient re-initiates treatment later on – after a treatment gap of ≥ 12 months –, (s)he may re-enter the cohort at that time (an indicator variable will be created to identify such patients, known as former users).
- 18 years or older at the time of treatment initiation
- CHA₂DS₂-VASc score³ ≥ 1

Exclusion criteria:

- patients with less than 12 months continuous enrollment in the study database without anticoagulant use before the first dispensing of anticoagulant medication.
- Patients with missing or ambiguous age or sex information.
- Patients with documented evidence of valvular disease defined as at least 1 inpatient or outpatient ICD-9 Dx code of [R11-4334]
 - 394.x (diseases of mitral valve)
 - 395.x (diseases of aortic valve)
 - 396.x (diseases of mitral and aortic valve)
 - 397.x (diseases of other endocardial structures)
 - 398.9x (other and unspecified rheumatic heart diseases)
 - V42.2 (heart valve replaced by transplant)

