3.2.1 Study size

This study will be estimating anticoagulant utilization parameters within a sampled population. The precision of these estimates will depend on the numbers of patients on which the estimate is made, and features of the estimate itself. The number of patients receiving anticoagulant medication and meeting study selection criteria is unknown at this stage. However, we assume that between 10,000 and 15,000 patients per year will meet selection criteria as having used warfarin or a newer anticoagulant so that by the end of the study (data from 2009-2015), there will be a total of at least 100,000 patients in each data source. (source: These are projections based on preliminary counts in the available UnitedHealth data)

The precision of proportion estimates (e.g. prevalence) is a function of the proportion and the number of patients contributing to the proportion (precision = standard error = $\sqrt{p(1-p)/n}$). As indicated in the table below, across a range of estimates provided, the precision for a prevalence estimate of 10% or 20% is less than 5% even for sample sizes that will likely be present in subgroups described in this study.

Table 1 Precision of estimates for proportion measures

Numerator	Denominator	Prevalence	95% CI	Precision (s.e.)
10	100	10%	4.9%-17.6%	3.0%
100	1,000	10%	8.2%-12.0%	0.9%
1,000	10,000	10%	9.4%-10.6%	0.3%
10,000	100,000	10%	9.8%-10.2%	0.1%
20	100	20%	12.7%-29.2%	4.0%
200	1,000	20%	17.6%-22.6%	1.3%
2,000	10,000	20%	19.2%-20.8%	0.4%
20,000	100,000	20%	19.8%-20.2%	0.1%

For continuous measures such as medication possession ratio ((MPR), see [Table 3](#)), the precision depends on the number of subjects on whom the estimate is made and the variability of the measures (precision = standard error = $\sqrt{\text{standard deviation}^2/n}$). As indicated in the table, the precision for a continuous measure is 5% or less even for measures that apply to strata that represent subgroups to be defined in this study.

Table 2

Precision of estimates for continuous measures

Sample Size	Mean	SD	Precision (s.e.)
100	1	0.5	5.0%
1,000	1	0.5	1.6%
10,000	1	0.5	0.5%
100,000	1	0.5	0.2%

By the end of the study, with a projected 100,000 patients meeting selection criteria, the various adherence measures will be estimated with a precision of 1% or less, except within fairly small strata.

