3.4 OUTCOMES

Patterns of anticoagulant medication use will be identified on the basis of a pharmacy dispensing. Pharmacy dispensing is considered the most accurate utilization measure short of electronic pillcounting caps. [\[R13-0543\]](#)

The primary outcomes considered include the proportion of patients dispensed specific anticoagulants and anticoagulant doses (for NOAC), as well as a description of the characteristics of these patients.

In addition, a variety of measures will be derived from features of the dispensing data, including: number of dispensings, characteristics of dispensings (dose, and days supplied), along with persistence measures (e.g., proportion with a single dispensing, proportion remaining on therapy over time, time until treatment switch or discontinuation). [\[R13-0542; R12-3689; P06-11504\]](#)
Treatment persistence over time constitutes the secondary outcome,

Table 3

[figure not shown]
Definition of utilization measures

Measure	Definition
Days supplied*	Number of days supplied by a dispensing
Dose**	Presumed dose based on # tablets, mg per tablet, and number of days
One dispensing only	Number (and fraction) of first anticoagulant recipients with no second dispensing
Persistence	Fraction of anticoagulant users with continued dispensings. Patients will be classified as persistent if they possess medication at the specified time point. Grace period of 14 days will be allowed to obtain an additional refill.
Anticoagulant switch	Dispensing of another anticoagulant within <30 days of the end of days supplied of the previous medication
Anticoagulant discontinuation	Treatment gap of ≥ 30 days (i.e., no dispensing of anticoagulant medication within 30 days of the end of days supplied)

*: Days supply likely reflects use patterns in a commercial insurer such as United Health or MarketScan.

**: Estimation of dose will be challenging during the dose titration period for warfarin. We explore warfarin dose over time and assess the feasibility of estimating average dose, seeking to identify maintenance dose (i.e., dose needed for consistent therapeutic INR).

***:

Notes:

Incident user: Patient with no dispensing of an oral anticoagulant in the prior 12 months

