Data prior to the launch of dabigatran in October 2010 will be used to characterize warfarin patients before the NOACs became available, and to evaluate the potential shift in patient characteristics over time. A comparison of patient characteristics across treatment groups will only be conducted within a common time window.

Secondary outcomes:

Utilization measures: Non-persistence

To ensure a valid comparison of utilization measures ([Table 3](#)), patients exposed to the various NOACs will be matched to warfarin on an exposure propensity score (PS) in a 1:1 fixed ratio using a nearest neighbor technique and a caliper of 0.05. In addition, the patients

will be matched within calendar quarters (3 month periods).

Briefly, all covariates listed in [REDACTED] will be included in a logistic regression propensity score (PS) model without further variable selection. In addition to demographic information, variables included in the PS were identified based on the a-priori expectation that they might be both associated with choice of anticoagulant and risk factors for study outcomes so that they represent likely confounding variables in a comparative safety and effectiveness analysis. The underlying assumption is that these variables capture the most important predictors of treatment persistence.

Balance of baseline characteristics in the matched cohorts will be evaluated. The utilization measures included in [Table 3](#) will be described for the PS-matched cohort. To properly account for differential follow-up, survival type analyses (i.e., Kaplan-Meier) will be used to describe time from treatment initiation to non-persistence (discontinuation or switch).

Number of patients at risk for this treatment outcome will be provided at 3-month intervals.

The various analyses are summarized below:

Analysis	Population	Outcome measure	Outcome type
Treatment initiation over time	Source population	Yearly initiation rate	Primary
Characteristics of anticoagulant users	Treatment cohort - Unmatched - Matched	Baseline characteristics	Primary
Utilization measures	Matched treatment cohort	- Treatment non-persistence (KM)	Secondary

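### Does leaving the estimator for the separate switch and discontinuation curves unstated make Core Figures 1 and 2 wrong?

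*Combined protocol and SAP*

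**What the plan says.** Section 3.6.1 describes the secondary outcome in the matched cohort: "survival type analyses (i.e., Kaplan-Meier) will be used to describe time from treatment initiation to non-persistence (discontinuation or switch". The summary of analyses at the end of that section again lists Kaplan-Meier against non-persistence only.

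The core figures in Appendix 1 (Section 11.1) go further. Figure 1 is "Cumulative incidence of treatment switches - 30 day gap", Figure 2 is its counterpart for discontinuation, and Figure 3 combines the two. The synopsis likewise lists "Time until treatment switch" apart from time to discontinuation. No visible passage gives an estimator for Figures 1 and 2, or says how the other event is treated.

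Three definitions bear on the point:

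- Switch (Section 3.4, Table 3): "Dispensing of another anticoagulant within <30 days of the end of days supplied of the previous medication".
- Discontinuation (same table): "no dispensing of anticoagulant medication within 30 days of the end of days supplied".
- End of follow-up (Section 3.2): "follow-up will end when there is a treatment gap of" 30 days or more.

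Core Tables 7 to 12 sort patients into continuers, switchers and discontinuers at 3, 6 and 12 months; Table 12, for example, anchors its look-back on "day of switch, day of discontinuation, day 360 for continuers". On precision, Section 3.2.1 expects that "the various adherence measures will be estimated with a precision of 1% or less, except within fairly small strata".

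**The concern.** Kaplan-Meier is the only time-to-event method in the visible text, so an analyst might use it for all three figures. For Figure 1 that would mean censoring patients when they discontinue. Censoring treats them as still able to switch later, but the definitions rule that out within the episode and follow-up has ended. One minus Kaplan-Meier would then lie above the real proportion of initiators who switch.

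The stakes would be practical. Section 3.6.1 builds the matched cohort so that utilization can be compared fairly across drugs, and the figures recur in each report. If drugs differ in how often patients stop, the size of the error differs too, and with samples this large a gap of two or three points would not be put down to chance.

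**Working it through.** **1. The plan's own precision figure.** Table 1 uses √(p(1−p)/n). For 1,000 of 10,000, √(0.1 × 0.9 / 10,000) = 0.003, or 0.3%, as printed. This is sampling error; it sets no tolerance for bias.

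**2. Are the events competing?** For Figure 1, yes. At the end of a supply, either another anticoagulant is dispensed in time (switch) or none is (discontinuation), and a discontinuation closes the episode. For Figure 2 it is less clear: Table 3 lets a switcher later stop all anticoagulants, and no visible passage ends follow-up at a switch.

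**3. Formulas.** The documents give no switch or discontinuation rates, so constant hazards are assumed: s for switch and d for discontinuation, per year, with t in years.

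- Proportion who have switched (competing-risk cumulative incidence, the Aalen-Johansen target): s/(s+d) × [1 − exp(−(s+d)t)].
- One minus Kaplan-Meier with discontinuers censored: 1 − exp(−s·t).

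**4. Illustration with s = 0.15, d = 0.7.**

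| Time | Cumulative incidence | 1 − Kaplan-Meier | Excess (points) |
|---|---|---|---|
| 3 months | 3.4% | 3.7% | 0.3 |
| 6 months | 6.1% | 7.2% | 1.1 |
| 12 months | 10.1% | 13.9% | 3.8 |

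At 12 months: 0.15/0.85 × (1 − e^−0.85) = 0.1010, against 1 − e^−0.15 = 0.1393.

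**5. Range.** Over s = 0.10 to 0.20 and d = 0.4 to 0.9, the excess is 0.1 to 0.5 points at 3 months, 0.5 to 1.8 at 6 months and 1.6 to 6.0 at 12 months.

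**6. Does the error always grow with discontinuation?** At a fixed switch hazard, yes. Across drugs with different switch hazards, not in absolute points. At 12 months, s = 0.20 with d = 0.4 gives 18.1% against 15.0%, an excess of 3.1 points; s = 0.10 with d = 0.7 gives 9.5% against 6.9%, an excess of 2.6. The drug with more discontinuation has the smaller error.

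**7. Would it create a false difference between drugs?** Take two drugs with the same 12-month cumulative incidence of switch, 10%, and d = 0.4 and 0.9. This needs s = 0.1288 and 0.1624. One minus Kaplan-Meier reads 12.1% and 15.0%, a gap of 2.9 points. The difference in error between the drugs is 0.3 points at 3 months and 0.9 at 6 months. But the switch hazards do differ, by 0.1624/0.1288 = 1.26, or 26%, so the gap reflects a real difference in switching rate.

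Conversely, give two drugs the same switch hazard, −ln(0.90) = 0.105, and discontinuation hazards −ln(0.70) = 0.357 and −ln(0.40) = 0.916. Kaplan-Meier reads 10.0% for both, while the cumulative incidences are 8.4% and 6.6%. A simulation of 400,000 patients agrees: 10.1% against 8.5%, and 10.0% against 6.6%. The two curves answer different questions.

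**8. Would a wrong choice show?** With s = 0.15 and d = 0.7 at 12 months, the composite in Figure 3 is 1 − e^−0.85 = 57.3%. First-event cumulative incidences add up to it: 0.1010 + 0.4715 = 0.573 after rounding. Two Kaplan-Meier curves, each censoring the other event, give 0.1393 + 0.5034 = 0.643. The 7-point mismatch would be visible across the three figures of one report.

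**The case for a change.** The best case for a change is that the wording of the titles does not settle the method. Figure 3 is also called a cumulative incidence, and its named method is Kaplan-Meier. The direction of the error does not depend on the assumed rates. A descriptive study still has to report the right proportion for each drug, so the statement in Section 8 that tables make no explicit comparisons is no answer. A sentence or two would remove the doubt.

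Much of this stands: the titles alone are not decisive, the direction is certain if discontinuers are censored, and the descriptive aim would not excuse a wrong curve. What is missing is a plan statement that leads to the error. Both visible mentions of Kaplan-Meier concern the composite, where both events count and none is censored as competing. The published copy also has blanks in Section 3.6.1, the change table and the core table list, so silence here cannot be read as an omission from the full plan. The claims about size are weaker still: they rest wholly on assumed rates, the link with discontinuation can reverse, and the two-drug gap is not clearly false.

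**Conclusion.** The concern identifies an unstated method for two appendix figures, not a rule that gives a wrong result. If discontinuers were censored in a Kaplan-Meier switch curve, it would run about 1.6 to 6.0 points too high at 12 months as a proportion of initiators, given constant hazards of 0.10 to 0.20 (switch) and 0.4 to 0.9 (discontinuation) per year. All of these are assumptions that the documents can neither support nor refute.

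No change follows. Estimating a cumulative incidence where one event precludes the other is routine, the choice can be made in programming without new data, and the composite curve offers a check if Figure 2 is a first-event measure. The secondary outcome, time to discontinuation or switch, is correctly paired with Kaplan-Meier and is untouched. A reader of the reports should simply check which estimator sits behind Figure 1, and whether Figure 2 counts discontinuation after a switch.
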